## **1. Introduction**

### **1.1 Preface**

This document was prepared by [name] (Statistician) in collaboration with [name] (Medical Statistician at the Centre for Statistics in Medicine, CSM). The content will be discussed with [name], Chief Investigator, [name], Trial Manager, and [name], Data manager. [name], [name], [name], and [name] will review and sign off the final version of this Statistical Analysis Plan (SAP). [name] will be responsible of implementing the SAP. [name] will be responsible of calculating total scores of the different instruments assessed in the RCT (described in Section 4). Any decisions that need to be made during the analysis will be discussed with [name].

### **1.2 Purpose and scope of the plan**

This document was prepared following the Primary Care Clinical Trial Unit (PC-CTU) Statistical Analysis Plan template (ref. TEMST01-A; version 1.0), which is based on ICH Topic E9 Statistical Principles for Clinical Trials, Step5, September1998; ICH Topic E3 Structure and content of Clinical Study Reports, July 1996; and PSI Guidelines for Standard operating procedures for good statistical practice in clinical research, version 6, 2000. It details the proposed analysis of primary, secondary and exploratory objectives for the Oxford Community Treatment Order Evaluation Trial (OCTET). Most of its content is derived from the OCTET Protocol Version 6. Subsequent analyses of a more exploratory nature will not be bound by this strategy, though they are expected to follow the broad principles laid down here. The principles are not intended to curtail exploratory analysis nor to prohibit accepted practices (for example, data transformation prior to analysis), but they are intended to establish the rules that will be followed, as closely as possible, when analysing and reporting the trial.

The statistical analysis plan will be available on request when the principal papers are submitted for publication in a journal. Suggestions for subsequent analyses by journal editors or referees, will be considered carefully, and carried out as far as possible in line with the principles of this analysis strategy; if reported, the source of the suggestion will be acknowledged. Any deviations from the statistical analysis plan

will be described and justified in the final report of the trial. The analysis of health economic data is not included in the scope of this document.

### **1.3 Changes from planned analysis in the protocol**

The analyses detailed within this document are in line with the spirit of the analyses detailed in the protocol however changes have been made to the types of statistical models or tests performed to allow for more sophisticated adjusted regression models to be used as the primary comparisons with the simpler unadjusted tests used for secondary sensitivity analyses. Adjusted regression models have more statistical power (are more precise) than unadjusted tests such as t-tests and thus make better use of the data collected.

The protocol makes reference to minimisation factors. However no minimisation procedure was carried out during treatment assignment. Instead a stratified block design was used.

Tertiary outcomes were specified. In particular, satisfaction with service is now being considered a tertiary outcome instead of a secondary outcome.

Analysis excluded:

There will be no analysis of the effect of discipline of clinical supervisor in readmissions as information on this outcome was not available.

## ***2. Trial overview***

### **Trial summary**

Different forms of compulsory supervision and treatment of outpatients with severe mental illness have developed internationally in the wake of widespread deinstitutionalisation. Community Treatment Orders (CTOs) for patients with psychiatric illness became available in 2008 as a treatment option in England and Wales under the amended Mental Health Act 2007. There is no convincing experimental evidence for the efficacy of compulsory outpatient treatment, so current clinical guidance and decision making is not based on firm evidence. Section 17 Leave remains a lawful option for supervision of patients in the community. OCTET

aims to demonstrate whether CTOs reduce readmissions to hospital in patients compared with patients not subject to CTOs.

## **Study objectives**

### *Primary objective*

To test the hypothesis that the use of CTOs in patients with psychosis and a history of compulsory admissions will result in a reduction in readmissions to hospital compared to treatment on leave.

### *Secondary objectives*

To investigate whether the use of CTOs in patients with psychosis and a history of compulsory admissions, compared to leave, will improve treatment adherence with a consequent reduction in relapse and readmission rates and improvement in social stability.

### *Exploratory objectives*

## **Sub-group analysis**

To identify the baseline characteristics of patients which are associated with differential treatment effect in subgroup analyses.

## **Readmission predictors**

To examine the factors (other than treatment group) associated with readmission.

## **Mediation analysis**

To explore the effect on readmission of process variables such as rate of contact and type of contact (i.e face-to-face vs. telephone contact).

## **Outcome measures**

### *Primary outcome*

The primary outcome measure is: psychiatric hospitalisation in the 12-month follow-up period (i.e. from INDEX to 365 days). This is a binary outcome: 1=Patient readmitted at all; 0=Patient never readmitted. A hospitalisation will be defined as the period between the patient's admission date and the date on which the patient leaves

hospital, which should include at least one overnight stay. Hospitalisations can be either voluntary or involuntary.

Recall to hospital of a patient on CTOs will not be classified as readmission (it will be understood as part of the treatment regime). If a recall ends in the CTO being revoked, this will be calculated as a readmission. Any patient who was never initially discharged from hospital after randomisation and remained hospitalised for 365 days after randomisation will be counted as a readmission.

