### *Secondary outcomes*

Secondary outcomes related to readmission follow the same readmission definition and constraints stated for the primary outcome. Secondary outcomes considered in this study are mainly obtained from medical records. They represent patterns of readmission and are listed next.

**Number of nights in psychiatric hospitalization from INDEX to 365 days.** This will include voluntary and involuntary hospitalizations. Nights on recall will not be included.

**Number of nights to first readmission from INDEX to 365 days.** Time to first readmission for patients (in both arms) that remained in hospital for the duration of the trial will be counted as zero. Nights on recall do not count as a readmission.

**Number of readmissions from INDEX to 365 days.** This will include voluntary and involuntary hospitalisations but not nights on recalls.

**Time under legal compulsion.** This will be measured by time being subject to the Mental Health Act (i.e. under sections 2, 3, 17, 37 or on a CTO).

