### **Method for handling time-varying interventions**

CTO is a time varying intervention. The MHA permits a CTO recall to continue for up to 72 hours (i.e. up to 3 nights in hospital) after which the patient either returns to the community on the CTO or the CTO is revoked and the patient remains in hospital under section 3. Recalling patients is therefore a part of the CTO treatment regime which sometimes results in an overnight stay at hospital and thus could be a confounder for the primary outcome. A sensitivity analysis will be carried out adjusting for the number of recalls in the CTO arm.

A secondary sensitivity analysis will be conducted adjusting the primary outcome by the time spent on Section 17 before starting on CTO for those patients with a delayed initiation after allocation.

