### **Description of treatments received**

For CTOs, the number of recalls and their lengths will be summarized. For both treatments, the time to initial discharge after randomisation and subsequent occurrences will be summarized according to:

- Number of hospitalisations;

- Average length of hospital stays;
- Changes to legal status;
- Total number of tribunals (MHRT);
- Total number of Managers Hearings;
- Number of recalls and revocations;
- Discharges;
- Average duration on CTO and on Section 17 Leave;
- Number of people who never leave hospital during the trial period;
- Number of patients whose voluntary hospitalisation is made involuntary during admission;
- Average number of service contacts received;
- Time under legal compulsion (including recalls);
- Number of
  - Face-to-face contacts with service;
  - Phone contacts with service.

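### The planned adjustment for number of recalls does not test the rule that leaves unrevoked CTO recalls out of the readmission count; an analysis that counts overnight recalls would

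*SAP*

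**What the plan says.** Under Primary outcome (SAP section 2), a hospitalisation runs from the admission date to the date the patient leaves "hospital, which should include at least one overnight stay". The section adds: "Hospitalisations can be either voluntary or involuntary". One kind of return is then exempted: "Recall to hospital of a patient on CTOs will not be classified as readmission". The reason given is that recall belongs to the treatment regime. The exemption has a limit: "If a recall ends in the CTO being revoked, this will be calculated as a readmission".

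Under Secondary outcomes, the readmission-based measures inherit this definition. For nights in hospital the SAP states: "Nights on recall will not be included". Recalls are also left out of time to first readmission and number of readmissions.

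Under Method for handling time-varying interventions (section 5), the SAP explains: "The MHA permits a CTO recall to continue for up to 72 hours (i.e. up to 3 nights in hospital"). After that the patient either goes back to the community on the CTO or the CTO is revoked. The section recognises that recall "sometimes results in an overnight stay at hospital and thus could be a confounder for the primary outcome" and answers with a sensitivity analysis adjusting for the number of recalls in the CTO arm.

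Under Description of treatments received (section 6): "For CTOs, the number of recalls and their lengths will be summarized".

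**The concern.** Two patients may each spend two nights back in hospital. If one is on a CTO, is recalled and is not revoked, that patient has no event. If the other is not on a CTO, the general definition makes the stay an event. Legal status is what the trial randomises, so the coding of the outcome is tied to the treatment under test. For patients on a CTO the exemption works in one direction only: it removes events, which is the direction of the primary hypothesis.

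The SAP sees that overnight recalls matter, but it treats the matter as confounding when it is one of outcome coding. As planned, a reader who asks whether a lower CTO readmission rate depends on the recall rule will find no analysis that answers. The other supporting analyses (unadjusted for stratification factors; adjusted for time on Section 17 before a delayed CTO start) do not recode recalls either.

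**Working it through.** **1. The plan's own figure.** Sample size determination gives 288 patients for a 16-point difference at 5% significance and 80% power, without stating the control risk. The usual formula is n per arm = [1.96·√(2p̄q̄) + 0.842·√(p₁q₁ + p₂q₂)]² / 0.16². The total is 284 at a control risk of 45%, 292 at 48% and 288 at 70%. So 288 fits more than one control risk, and the control risk has to be assumed. It is not disputed here.

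**2. Inputs.**
- 165 per arm: the target of 330, allocated 1:1 (section 3).
- Control risk p: assumed 36% to 67%. At 48.65% and at 67%, 144 per arm gives about 79% power for 16 points, close to the stated 80%. The 36% is a lower value chosen to show the range.
- Uncounted share x, the proportion of the CTO arm whose only overnight return is an unrevoked recall: assumed 2%, 5% and 8%, since the SAP gives no recall rate.
- No crossover, and the true rate of overnight return is equal in both arms. Each uncounted recall therefore stands in for an admission one-for-one.

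**3. Formula.** The counted CTO risk is p − x, so RR = (p − x)/p. The rejection rate of the two-sided test is 1 − Φ((c − x)/SE₁) + Φ((−c − x)/SE₁), with c = 1.96·√(2p̄q̄/165) and SE₁ = √[p(1−p)/165 + (p−x)(1−p+x)/165].

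Example with p = 0.36, x = 0.05: RR = 0.31/0.36 = 0.86; p̄ = 0.335; c = 1.96 × 0.0520 = 0.1018; SE₁ = 0.0519. Rejection = 0.159 + 0.002 = 16%.

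| x | p = 36% | p = 48.65% | p = 67% |
|---|---|---|---|
| 2% | RR 0.94, 6.7% | RR 0.96, 6.5% | RR 0.97, 6.7% |
| 5% | RR 0.86, 16% | RR 0.90, 15% | RR 0.93, 16% |
| 8% | RR 0.78, 34% | RR 0.84, 31% | RR 0.88, 32% |

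At 5% and 8%, nearly all rejections favour CTO.

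**4. Does the planned adjustment help?** Recall count can be above zero only for someone on a CTO. In a regression on both arms, the adjusted treatment effect therefore compares CTO patients without a recall with the whole Section 17 arm. Suppose half of each arm returns, x = 5%, and a further 20% of the CTO patients with a counted readmission also have a recall (0.45 × 0.20 = 9%). The recall-free CTO patients are 1 − 0.05 − 0.09 = 0.86 of the arm, and their risk is (0.50 − 0.05 − 0.09)/0.86 = 0.42. The ratio to 0.50 is 0.84, further from 1 than the unadjusted 0.90.

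A simulation of these settings (144 per arm, 1,500 trials, Poisson regression with robust errors) gave:

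| x | Unadjusted RR | Adjusted for recall count | Overnight recalls counted |
|---|---|---|---|
| 5% | 0.90 | 0.85 | 1.00 |
| 10% | 0.80 | 0.78 | 1.00 |

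The adjusted values depend on the assumed 20%. The recode returns 1.00 because the equal true rates were built in. What the exercise shows is that the adjustment does not undo the exemption. If the adjustment is instead meant within the CTO arm alone, it yields no comparison between arms.

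**5. Nights in hospital.** With one uncounted recall of at most 3 nights in 5–8% of CTO patients, the CTO mean falls by at most 0.05 × 3 = 0.15 to 0.08 × 3 = 0.24 nights. The SAP's detectable difference is 14 days, so this effect is negligible.

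**The case against.** The strongest reply is that the rule is a reasoned, disclosed choice. Recall is a feature of the CTO, it is short, and a recall that turns into a real admission through revocation does count. Recall numbers and lengths will be reported. All of this stands, and it is why the primary definition need not change.

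A second reply concerns the one-for-one assumption. Recall is open only to patients on a CTO. If some recalls are extra events that would not otherwise have been admissions, the present rule may be unbiased for admissions, and counting recalls would then lean against CTO. This also stands. The percentages above are therefore not error rates of the SAP's own outcome; they hold only under the stated assumption.

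A reader might infer something stronger: that the definition differs by randomised arm, that every short return from Section 17 leave counts, and that all four readmission-based outcomes are materially tilted. The document does not support this. The exemption attaches to being on a CTO, and since clinicians may change legal status and analysis is by allocation, a Section 17 patient later placed on a CTO has it too. The SAP does not say how a return from leave is classified; that it counts is inferred from the general definition and the lack of an exemption. The effect on nights is negligible.

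None of these replies rescues the recall-count adjustment, which does not address the question it was added for.

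**Conclusion.** The point holds in a limited form. Unrevoked overnight recalls are left out of the primary outcome, time to first readmission and number of readmissions. For patients on a CTO this can only lower the count, and the one analysis meant to examine it cannot do so.

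The size cannot be fixed from the document. Under one-for-one replacement, 165 per arm and control risk 36–67%, it runs from minor (2% uncounted: RR 0.94–0.97, about 6.5–7% rejection) through 5% (RR 0.86–0.93, 15–16%) to 8% (RR 0.78–0.88, 31–34%). If recalls are additional events, the bias is smaller or absent.

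The SAP gives no ground for concluding that a lower CTO rate would be an artefact. The conclusion is only that the planned analyses could not show whether it was. The sensitivity analysis should be changed; the primary definition can stay.

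**What to change.** In Method for handling time-varying interventions, replace the adjustment for number of recalls with a pre-specified sensitivity analysis of the primary outcome, time to first readmission and number of readmissions. In it, every recall that includes an overnight stay counts as a readmission, whichever arm the patient was randomised to, and the models are otherwise unchanged. Report it next to the primary result and describe it as a bound, since it may overcount against CTO where a recall would not otherwise have been an admission.

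The cost is a change of SAP wording, some recoding from recall data that the SAP already plans to derive and summarise, and an extra set of result rows. No new data collection is needed.

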### *Secondary outcomes*

Secondary outcomes related to readmission follow the same readmission definition and constraints stated for the primary outcome. Secondary outcomes considered in this study are mainly obtained from medical records. They represent patterns of readmission and are listed next.

**Number of nights in psychiatric hospitalization from INDEX to 365 days.** This will include voluntary and involuntary hospitalizations. Nights on recall will not be included.

**Number of nights to first readmission from INDEX to 365 days.** Time to first readmission for patients (in both arms) that remained in hospital for the duration of the trial will be counted as zero. Nights on recall do not count as a readmission.

**Number of readmissions from INDEX to 365 days.** This will include voluntary and involuntary hospitalisations but not nights on recalls.

**Time under legal compulsion.** This will be measured by time being subject to the Mental Health Act (i.e. under sections 2, 3, 17, 37 or on a CTO).

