#### **Target population**

##### *Inclusion criteria*

Patients were eligible if they were:

- Aged 18-65 years (in line with local administrative procedures for adult mental health services);
- Diagnosed with psychosis;
- Currently admitted under section 3 or section 37 (without restrictions) of the MHA;
- Not currently subject to any other legal restrictions;
- Judged by their clinicians (RC and AMHP) to need ongoing community treatment, but, having considered the relevant legal standards and clinical indicators, clinicians are genuinely uncertain as to which treatment mechanism would be appropriate;
- Able to consent to take part in research and give written and informed consent;
- Not having participated in the study (i.e. people with multiple admissions throughout the recruitment period should only participate in the study once).

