### **Timing of data collection**

Recruitment took place from 10 November 2008 to 22 February 2011. Potential participants were identified, informed of the trial and asked for consent prior to randomisation. The follow-up data were planned to be collected at six months after randomisation and at 12 months after randomisation.

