### **Secondary analysis**

Secondary analyses will be conducted using the ITT population. No adjustment for missing data will be performed when analysing these outcomes as no missing data is expected for them.

Secondary outcomes will be analysed in the same way as primary outcomes using multiple regression models with adjustment for stratification factors. The type of regression model will depend on the data distribution. All model assumptions will be assessed.

Number of readmissions and number of nights in psychiatric hospitalization are count outcomes and will be analysed using Poisson or negative-binomial regression models depending on data dispersion. Results will be presented as incident-density ratios, which are interpreted in the same way as relative risks.

The number of nights to first readmission from INDEX to 365 days, and time under compulsion, are time to event outcomes and analyses will be performed using proportional hazards regression, with results presented as hazard ratios with 95% confidence intervals. Kaplan Meier plots will also be presented and the median time to readmission calculated with 95% confidence intervals.

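### Time to first readmission starts at randomisation, when patients are still inpatients, and scores the never-discharged as zero; nothing pre-specified separates later discharge from prevented readmission

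*SAP*

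**What the plan says.** **Outcome.** The SAP (Secondary outcomes) lists "Number of nights to first readmission from INDEX to 365 days". Under Secondary analysis it adds that "The number of nights to first readmission from INDEX to 365 days, and time under compulsion, are time to event outcomes", to be analysed by proportional hazards regression with Kaplan-Meier plots and a median time to readmission.

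**Clock.** INDEX is not defined. The primary outcome uses the same window, "psychiatric hospitalisation in the 12-month follow-up period (i.e. from INDEX to 365 days". Three places point to randomisation as day 0:
- Primary outcome counts as readmitted any patient "never initially discharged from hospital after randomisation and remained hospitalised for 365 days after randomisation".
- Timing of data collection: "The follow-up data were planned to be collected at six months after randomisation and at 12 months after randomisation".
- Description of treatments received: "the time to initial discharge after randomisation and subsequent occurrences will be summarized".

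**Status on day 0.** One inclusion criterion is "Currently admitted under section 3 or section 37 (without restrictions) of the MHA", so both arms start in hospital.

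**Never-discharged patients.** "Time to first readmission for patients (in both arms) that remained in hospital for the duration of the trial will be counted as zero". Secondary readmission outcomes follow the primary readmission definition, so these patients are events at night zero.

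**Related analyses.** Time to initial discharge is summarised only. The sensitivity analysis for delayed CTO start concerns the primary outcome and time on Section 17 before the CTO. The other primary sensitivity analysis removes the stratification factors.

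**The concern.** A patient cannot be readmitted before leaving hospital, yet the clock is already running. Two patients show the effect:
- Discharged on day 300, readmitted on day 310: scores 310 nights, of which 10 were in the community.
- Discharged on day 5, readmitted on day 100: scores 100 nights, of which 95 were in the community.

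The first looks far better on the planned scale and did far worse at staying out.

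The zero rule fits a different clock. Zero is the number of community nights of someone who never left, but it is not their number of nights since randomisation. The two conventions meet in a jump at day 365.

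Discharge happens after randomisation, and the arms are two legal routes out of hospital, so the delay could differ between them. If it does, the hazard ratio mixes a discharge effect with a readmission effect, and the trial's question concerns the second.

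**Working it through.** **The plan's own figures.** The SAP states no figure for this outcome. Its 288 patients are for a 16-point difference in the 12-month proportion. The control rate is not given; without continuity correction, 288 is reproduced at a control rate of about 46% or 70% (two-sided 5%, 80% power, 1:1). That does not bear on the clock; the 16 points serve below only as a yardstick.

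**The discontinuity (no assumption on delays).**

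| Patient | Time | Status |
|---|---|---|
| Discharged day 364, not readmitted | 365 | censored (best) |
| Still in hospital at day 365 | 0 | event (worst) |

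**Null model for the bias.** The SAP gives neither discharge delays nor post-discharge rates, so both are assumed.
- Readmission hazard after discharge is equal in the two arms: λ = −ln(1 − 0.40)/365 = 0.00140 per day.
- Time from randomisation to discharge is exponential; only its mean differs by arm.
- Never-discharged patients are events at night zero, entered as 0.5 night because the SAP does not say how a zero time enters the model.
- The true hazard ratio after discharge is 1. Arms of 60,000 to 100,000 leave little simulation error.

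| Mean stay, later v earlier arm | HR, planned clock | HR, entry at discharge |
|---|---|---|
| 30 v 30 | about 1.0 | about 1.0 |
| 28 v 14 | 0.93 to 0.96 | about 1.0 |
| 60 v 30 | 0.89 to 0.91 | 0.98 to 0.99 |
| 90 v 30 | 0.85 to 0.87 | 1.00 to 1.01 |

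Ranges are across repeated runs. If the never-discharged are dropped instead of scored zero, 90 v 30 gives 0.81.

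**Other post-discharge rates.** Rates of 36%, 46% and 70% per year, with nobody left undischarged, give 0.86 to 0.89 for 60 v 30 and 0.74 to 0.80 for 90 v 30.

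**Effect of the zero rule (60 v 30, same three rates).** The never-discharged share was set directly.
- 2% in the later arm, 0% in the other: HR 0.89 to 0.95.
- 5% v 0%: HR 0.95 to 1.03.
- 2% or 5% in both arms: HR 0.86 to 0.91.

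The rule offsets the bias only when never-discharged patients cluster in the later-discharged arm.

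**Chance of a false finding.** The probability of a significant result favouring the later-discharged arm is Φ(½√D·|ln HR| − 1.96), where D is the number of events.
- D = 95, HR 0.89: ½ × 9.75 × 0.1165 = 0.57, so Φ(−1.39) = 8%.
- D = 130, HR 0.85: ½ × 11.40 × 0.1625 = 0.93, so Φ(−1.03) = 15%.

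The nominal figure is 2.5%.

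**Effect on the primary proportion.** With μ = 1/mean stay, the proportion readmitted by day 365 is 1 − [μe^(−365λ) − λe^(−365μ)]/(μ − λ). The never-discharged, e^(−365μ), are added under the SAP's rule.
- For a mean of 60: 1 − (0.016667 × 0.6 − 0.0013995 × 0.00228)/0.015267 = 34.5%, plus 0.2% = 34.7%.
- Means of 30 and 90 give 37.4% and 33.3%.
- The spurious gaps are therefore about 2.6 points (60 v 30) and 4 points (90 v 30), against the design's 16.

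**The case against.** **Randomisation is the right origin for an intention-to-treat comparison.** This stands. A discharge clock starts at an event that treatment may influence, so patients entering the risk set in the two arms need not be comparable. A reader might infer that the planned clock should be replaced. The documents do not support that: the SAP analyses all randomised patients, and the randomisation-clock result should remain the main one.

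**Some information on delay is already planned.** This partly stands. Time to initial discharge, length of stay and the number who never leave hospital will be summarised. Nights in hospital from INDEX are compared by arm, and the SAP claims 80% power for a 14-day difference in hospital days, so the larger assumed delays would probably show there. But a summary beside a hazard ratio does not say how much of that ratio the delay explains.

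**Zero is deliberate worst-outcome coding.** This is fair: it agrees with counting never-discharged patients as readmitted. It still leaves the jump at day 365 and does not touch the index nights of everyone else. Coding these patients as not readmitted would be no remedy. With mean stays of 90 v 30 days it widens the spurious gap in the primary proportion from about 4 points to nearly 6 (37.4% v 31.6%).

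**No passage shows that delays differ by arm.** Correct. The point is conditional on that.

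**Conclusion.** The point holds as a weakness in how a secondary outcome is fixed. The planned analysis counts index-stay nights as readmission-free for patients who are eventually discharged, scores the rest as failures at night zero, and pre-specifies nothing that separates later discharge from prevented readmission. Under equal hazards after discharge, a mean stay of 60 rather than 30 days moves the hazard ratio to about 0.9, and 90 rather than 30 days to about 0.85.

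These sizes rest on assumed exponential delays and an assumed 40% yearly readmission rate. That INDEX means randomisation is an inference, though three places in the SAP support it.

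A reader might infer that the analysis favours CTOs, or that the primary result is compromised. The documents support neither. They give no discharge times, so size and direction are unknown, and an uneven share of never-discharged patients can cancel the bias. The shift in the primary proportion is small beside 16 points even under large assumed imbalances.

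**What to change.** 1. **Secondary outcomes:** state that INDEX is the date of randomisation, if that is intended, and how a time of zero enters the model.
2. **Secondary analysis:** keep the randomisation-clock model on all randomised patients as the main analysis.
3. **Secondary analysis:** add a pre-specified proportional hazards analysis with delayed entry at first discharge, or a multi-state model with the index stay as its own state. Never-discharged patients contribute no time at risk of readmission; report their number by arm.
4. **Beside it:** report time from randomisation to first discharge by arm, with Kaplan-Meier curves and a hazard ratio.

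The cost is a few lines of text and two further models, using admission and discharge dates that the SAP already plans to process. The delayed-entry analysis conditions on a post-randomisation event, so label it as supporting and read it together with the discharge comparison.
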